### **5.0 ANALYSIS POPULATIONS**

Analysis populations will be defined in the following sections. In each analysis population, subjects will be analyzed at the dose level they were assigned to at the time of enrollment. The safety analyses will be performed on the All Treated Population. Primary efficacy analyses for ORR and DOR will be based on the Efficacy Evaluable Population. PFS and time to initial response analysis will be based on the All Treated Population. Response will be assessed by investigators. Response assessed by IRC is not available for the interim CSR but will be analyzed and included in the final CSR.

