### 11.2 Progression-free Survival (PFS)

PFS is defined as the time from the date of first dose to the date of first disease progression or death, due to any cause. If a subject does not experience any disease progression or death, the subject will be censored at the date of last adequate assessment (censoring date). If a subject receives an autologous or allogeneic stem cell transplant, the subject will be censored at the date of transplant. If a subject starts new anticancer therapy before disease progression or death, the subject will be censored at the date of last adequate assessment prior to receiving the new anticancer therapy. Adequate assessment is defined as physical examination (PE) and complete blood count (CBC) or computed tomography (CT) for CLL disease subgroups (or PET-CT for RS/PLL disease subgroup) and CBC. If a subject does not have any adequate assessment after first dose, the subject will be censored at Day 1.

PFS is calculated as date of disease progression or death (censoring date for censored subjects) - first dose date + 1.

Situation	Outcome	Date	Event Description/ Censoring Reason
Documented PD	Event	Earliest date of disease	PD

Events and censoring rules for PFS are summarized as follows:

CONFIDENTIAL

		assessment documenting PD	
Death	Event	Date of death	Death
Start of new anticancer therapy before documented PD or death	Censored	Date of last adequate assessment prior to receiving the new anticancer therapy	New anticancer therapy
Start of transplant	Censored	Date of transplant	Transplant
Withdrawal of consent before documented PD or death	Censored	Date of last adequate disease assessment	Withdrawal of consent
Loss to follow-up before documented PD or death	Censored	Date of last adequate disease assessment	Loss to follow-up
No documented PD or death and the reason for not completing Safety Follow-up visit is "Other"	Censored	Date of last adequate disease assessment	Other: specify
No documented PD or death at the time of data cutoff	Censored	Date of last adequate disease assessment	Data cutoff
No post-baseline adequate disease assessments	Censored	Date of first dose	No post-baseline adequate disease assessments

Kaplan-Meier (KM) curve will be used to estimate the distribution of PFS. Median PFS and the 95% confidence limits and PFS rates for selected landmarks with 95% confidence intervals will be reported. Number of progressions, deaths, and censored events by reason will be summarized.

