### 11.3 Duration of Response (DOR)

DOR is defined as the time from the date of achieving the first CR, CRi, or PR to the date of disease progression or death due to any cause, whichever comes first. Subjects who do not have a disease progression or death will be censored using the same rule for PFS as described in Section 11.2.

DOR is calculated as date of disease progression or death (censoring date for censored subjects) – date of achieving the first CR, CRi, or PR + 1.

Kaplan-Meier (KM) curve will be used to estimate the distribution of DOR. The same summary statistics for PFS will be presented for DOR.

For CLL disease subgroups (ie, except RS/PLL disease subgroup), DOR including PRL as one of the responses will also be summarized in the same fashion.

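### Two PFS censoring rules in SAP 11.2 (transplant, and no post-baseline assessment) lack the condition that no progression or death came first, so one subject can match both an event rule and a censoring rule

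*SAP*

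**What the plan says.** Section 11.2 defines the endpoint without any assessment requirement: "PFS is defined as the time from the date of first dose to the date of first disease progression or death, due to any cause". The general censoring sentence is conditional: "If a subject does not experience any disease progression or death, the subject will be censored at the date of last adequate assessment".

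Two further sentences carry no condition:

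- Transplant: "If a subject receives an autologous or allogeneic stem cell transplant, the subject will be censored at the date of transplant".
- No assessment: "If a subject does not have any adequate assessment after first dose, the subject will be censored at Day 1".

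The events and censoring table repeats the pattern. Its progression and death rows are plain events. Of its seven censoring rows, five carry a condition, for example "Start of new anticancer therapy before documented PD or death" and "No documented PD or death at the time of data cutoff". The transplant row and the row for no post-baseline adequate assessment carry none.

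On the population, Section 5.0 states: "PFS and time to initial response analysis will be based on the All Treated Population". Section 5.2 requires only one dose for that population. Only the Efficacy Evaluable Population (Section 5.3) needs a post-dose response assessment.

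**The concern.** Some subject histories satisfy an event rule and a censoring rule at once, and nothing in Section 11.2 says which prevails. Two programmers could derive different PFS times and statuses from the same data and both claim to have followed the SAP.

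The choice is not neutral. Resolving the conflict as censoring turns an observed event into a censored time, which can only leave the Kaplan-Meier estimate unchanged or raise it. PFS is one of the three measures named in the secondary objective (Section 2.0), and its median and landmark rates are to be reported. The planned summary of censoring by reason would show how many subjects fell under each rule, but would not correct the estimate.

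**Working it through.** **Step 1: the rules side by side (Section 11.2).** The SAP gives no figure to reproduce here, so the check starts with the text.

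| Censoring situation | Limited to subjects without prior progression or death? |
|---|---|
| New anticancer therapy | Yes |
| Transplant | **No** (text and table) |
| Withdrawal of consent | Yes |
| Loss to follow-up | Yes |
| Safety follow-up not completed, reason other | Yes |
| Data cutoff | Yes |
| No post-baseline adequate assessment | **No** (text and table) |

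Five rows are conditional and two are not. No hierarchy, row order or first-to-occur rule covers the table.

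**Step 2: histories that match two rules.**

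- *Death before any adequate assessment.* The death row gives an event at the date of death. The no-assessment row gives censoring at the first dose date. These subjects are in the analysis because it uses the All Treated Population.
- *Progression, then transplant.* The progression row gives an event at the earliest documenting assessment. The transplant row gives censoring at the later transplant date.

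**Step 3: illustrative size, early deaths.** Assumptions: N = 30 (the planned size of several expansion cohorts in Section 4.0), 15 PFS events by the landmark, no other censoring. The event count and the number of affected subjects are not from the SAP.

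Events first: 1 − 15/30 = 50.0%.

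If k of the 15 events are early deaths censored on Day 1, they leave both the event count and every risk set, so PFS = 1 − (15 − k)/(30 − k):

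- k = 1: 1 − 14/29 = 51.7%
- k = 3: 1 − 12/27 = 55.6%
- k = 5: 1 − 10/25 = 60.0%

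**Step 4: illustrative size, progression then transplant.** Same assumptions, with m progressors censored at transplant. If transplant comes before any other event, PFS = 1 − (15 − m)/(30 − m). If it comes after the landmark, these subjects count as event-free throughout and PFS = 1 − (15 − m)/30.

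| m | Transplant before other events | Transplant after the landmark |
|---|---|---|
| 1 | 51.7% | 53.3% |
| 2 | 53.6% | 56.7% |
| 3 | 55.6% | 60.0% |

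**Step 5: a second set of assumptions.** Let S be landmark PFS among subjects other than the k early deaths. Day 1 censoring reports S. Counting the deaths reports (1 − k/N) × S, so the gap is S × k/N. For N = 30 and k = 1 to 5:

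- S = 0.50: gap of 1.7 to 8.3 percentage points
- S = 0.80: gap of 2.7 to 13.3 percentage points

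For N = 65 (the planned size of cohort 2b), k = 3 and S = 0.50, the gap is 0.50 × 3/65 = 2.3 points. The direction is the same throughout. The size depends on cohort size and on counts the SAP does not give.

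**The case against.** The strongest reply is that Section 11.2 has a natural events-first reading. The definition runs to the first progression or death. The general censoring sentence applies only to subjects with neither. The progression and death rows are unqualified. On this view the Day 1 sentence merely supplies a fallback date for a subject already due to be censored, and the transplant sentence merely sets a different censoring date from the new-therapy rule. For a progressor, PFS time has ended before the transplant. Section 11.3 points the same way for DOR: "Subjects who do not have a disease progression or death will be censored using the same rule for PFS as described in Section 11.2".

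This reading is plausible, and under it there is no bias. But Section 11.2 never states it, and its own drafting undercuts it. The new-therapy sentence directly after the transplant sentence repeats its own condition, which would be redundant if the general sentence governed everything. Section 11.3 shows that the limit could be written out, but it governs DOR, not PFS.

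Three further points are fair:

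- Early deaths without an adequate assessment may be few in the CLL subgroups, where a physical examination with a blood count appears to suffice and the first post-dose haematology visit is nominally Study Day 28 (Appendix A). The exposed period would be longer in the RS/PLL subgroup if PET-CT is required, since the first nominal tumour assessment is Study Day 56.
- Five such deaths in 30 is a high assumed count, so the figures show direction and possible scale, not an expected effect.
- The study is nonrandomized, no formal hypothesis tests are planned (Section 6.1), and the SAP sets no decision threshold on PFS.

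These limit the consequence. They do not resolve the conflict between the rules.

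**Conclusion.** The concern holds. As written, the two rules are wrong for subjects with an earlier event, because they censor people whom the same section counts as events, and no precedence is stated. Such subjects can exist; the SAP does not show that any do.

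Under the Step 3 and 4 assumptions, literal use of the rules moves landmark PFS from 50.0% to between 51.7% and 60.0% for one to five early deaths, and over the same range for one to three transplanted progressors. The Step 5 assumptions give up to 13.3 points for five early deaths in 30. With no affected subjects, or with events-first programming, the effect is zero.

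DOR is not affected by the missing condition, because Section 11.3 censors only subjects without progression or death. The textual gap is certain; its effect on reported PFS is not known. It should be fixed because the ambiguity works in one direction only and is easy to remove.

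**What to change.** Amend both the text and the table of Section 11.2:

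1. State the precedence: the first documented progression or death is the event, unless new anticancer therapy or transplant started earlier.
2. Limit the Day 1 rule to subjects with no adequate post-baseline assessment who also have neither documented progression nor death. Keep the first dose date as their censoring date.
3. Limit the transplant rule to transplant that precedes documented progression or death. Keep the transplant date as the censoring date.

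If censoring early deaths on Day 1 is intended, the SAP should say so and justify it. Check the censoring sentence in Section 11.3 against the new precedence sentence, so that a responder who is transplanted and later progresses or dies is handled consistently in both sections.

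The cost is a few phrases in the SAP and a small change or check in the PFS derivation. No new data are needed. If the two rules had been programmed literally, the PFS estimate may become slightly less favourable.

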### 11.3 Duration of Response (DOR)

DOR is defined as the time from the date of achieving the first CR, CRi, or PR to the date of disease progression or death due to any cause, whichever comes first. Subjects who do not have a disease progression or death will be censored using the same rule for PFS as described in Section 11.2.

DOR is calculated as date of disease progression or death (censoring date for censored subjects) – date of achieving the first CR, CRi, or PR + 1.

Kaplan-Meier (KM) curve will be used to estimate the distribution of DOR. The same summary statistics for PFS will be presented for DOR.

For CLL disease subgroups (ie, except RS/PLL disease subgroup), DOR including PRL as one of the responses will also be summarized in the same fashion.

### 11.4 Time to Initial Response

Time to initial response of PR or better will be calculated as (date of first PR or better – date of first dose + 1) / 30.4376 and summarized using descriptive statistics. Time to initial response of PRL or better for CLL disease subgroups (ie, except RS/PLL disease subgroup) will also be summarized in the same fashion.

### **11.5 Subgroup Analysis**

### **12.0 SAFETY ENDPOINTS**

Safety will be assessed by evaluation of treatment-emergent adverse events, laboratory values, vital signs measurements, ECG results and physical exams.

### 12.1 Adverse Events

Adverse events (AEs) will be coded using the Medical Dictionary for Regulatory Activities (MedDRA v 24.0) reporting system. Treatment-emergent AEs are defined as those events that occur on or after the first dose of study drug, through the treatment phase, and within 30 days following the last dose of study drug.

The occurrence of treatment-emergent adverse events (TEAEs) and serious TEAEs will be presented respectively by SOC and PT. If a subject experiences the same event more than once, the event will be counted only once with the greatest severity. Additionally, TEAEs and serious TEAEs will be presented by relationship and by worst severity.

Fatal (Grade 5) AEs, AEs leading to study drug discontinuation, AEs leading to study drug interruption, and AEs leading to study drug modification will be summarized.

Events of clinical interest (ECI) will be summarized. Definition of each ECI is listed in Integrated Summary of Safety (ISS), Appendix B.

For ibrutinib intolerant cohorts (8a and 8b), ibrutinib related AE will be tabulated.

### 12.2 Hematology, Chemistry, and Immunology Parameters

Selected laboratory parameters such as AST, ALT, bilirubin, amylase, and lipase will be graded based on CTCAE 4.03. Hematologic toxicities in CLL patients will be graded by Hallek (2008) as specified in Appendix C and CTCAE 4.03. Shift tables will be presented to summarize grade shift from baseline to maximum post baseline grade. Graphs will be presented for mean or median of selected lab parameters over time as appropriate.

### T/B/NK/Monocytes Cell Counts

Plot for mean change over time and standard error of mean (SEM) at each time point will be presented for selected flow cytometry testing parameters, CD4+, CD8+, NK cells, and Monocytes.

### Serum Immunoglobulin

For IgG, IgM, and IgA levels, descriptive statistics will be presented at baseline, last post baseline, minimum post baseline, and maximum post baseline. Changes from baseline at each of the last, minimum, and maximum post baseline time points will be summarized.

### **Molecular Markers**

Molecular markers are collected at screening visit. Parameters to be summarized include 11q13 (CCND1), 13q14(D13S319), 13q34, 6q23 (MYB), ZAP70 (CLL), BCL6, Blasts Gate, CEP 12, CEP6(D6Z1), Granulocyte Gate, Immunoglobulin Heavy locus (IGH), Lymph Gate, MYC, MYD88, Monocyte Gate, Notch 1, Plasma Gate, SF3B1, Viability.

### 12.3 B Symptoms

Descriptive statistics will be presented for B-symptoms. For subjects who were symptomatic at baseline, sample size and percent of subjects with resolution at post baseline will be summarized by visit. For those who were as asymptomatic at baseline, sample size and percent of subjects with onset of symptoms at post baseline will also be summarized by visit.

### 12.4 Vital Signs and Physical Examinations

For each vital sign measurement, descriptive statistics will be presented at baseline, last post baseline, minimum post baseline, and maximum post baseline. Change from baseline at each of the last, minimum, and maximum post baseline time points will be summarized.

Findings of abnormal physical examinations will be tabulated by body system at each visit.

### 12.5 Prior and Concomitant Medications

Prior and concomitant medications will be coded according to the World Health Organization (WHO) drug dictionary. Medications started or ended prior to first dose will be considered as prior medications. Concomitant medication is defined as all medications used on or after the first dose, through the treatment phase, and for 30 days following the last dose of study drug. Using this definition, a medication can be classified as both prior and concomitant. Medications with completely missing start and stop dates will be considered as both prior and concomitant medications.

Appendix D shows the prior and concomitant medication flags for various scenarios. The number and percentage of subjects will be presented by anatomical therapeutic chemical (ATC) classification system Level 2 and preferred term.

### **12.6 Study Drug Exposure**

- Duration of exposure (months) is defined as (last dose date first dose date + 1) / 30.4375
- Total cumulative dose (g) is defined as total amount of dose received during the study period
- Average daily dose (mg/day) is defined as (actual cumulative dose (mg) / duration of exposures)
- Relative dose intensity is defined as (total cumulative dose (mg) / (duration of exposure (days) \* 1 (g) \* 2) \*100) Descriptive statistics will be presented for these values. Relative dose intensity will be calculated for Cohort 2b, 2c, 9, and 10 in which the intended dose regimen/level were never changed per protocol throughout the study.

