### STUDY SCHEMA FOR DOSE-ESCALATION COHORTS

Note: No DLTs occurred during dose escalation and the MTD was not reached. Under Amendment 4, subjects in Cohort 3 were switched to COL Under Amendment 5, subjects in Cohort 1, Cohort 2a, and Cohort 4a were switched to COL Under Amendment 6, subjects in Cohort 2c and in Cohort 4b COL Abbreviations: bid = twice daily; DLT = dose-limiting toxicity; MTD = maximum tolerated dose; qd = once daily

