Protocol amendment 5: The sample size was increased from 30 subjects to 200 subjects for cohort 2b (RR) and to 60 subjects for cohort 11 (TN) to provide safety and efficacy data in support of the Phase 3 program of acalabrutinib in CLL.

Protocol amendment 6: No change on sample size.

Protocol amendment 7: The sample size was decreased from 200 subjects to 65 subjects for cohort 2b (RR) which is considered sufficient to meet the primary objective of this study. The sample size for cohort 8b (II) was increased from 30 subjects to 35 subjects to obtain additional safety and efficacy data in ibrutinib intolerant population.

Protocol amendment 8-13: No change on sample size.

A total of approximately 286 eligible subjects were planned to be enrolled in this study.

Cohort	Dose Regimen	Treatment Phase	Disease Subgroup	Planned Sample Size*	Protocol Version the Cohort First Added	Revision History of Dose Regimen	Revision History of Sample Size
1	CCI	Escalation	RR	6	Original	CCI	
2a		Escalation	RR	6	Original		
3		Escalation	RR	6	Original		
4a		Escalation	RR	6	A2		
2b		Escalation / Expansion	RR	65	A2/A4		A2 (N=6) dose escalation $\rightarrow$ A4 (N=30) expansion $\rightarrow$ A5 (N=200) $\rightarrow$ A7 (N=65)
4b		Escalation	RR	6	A2		
2c		Expansion	RR	30	A4		
7		Expansion	TN	30	A3		$A3 (N=8-12) \rightarrow A4 (N=30)$
11		Expansion	TN	60	A4		$A4 (N=30) \rightarrow A5 (N=60)$
8a		Expansion	Ibr. Intol.	8-12	A3		A3 (N=8-12) $\rightarrow$ A4 subjects switched to 100 mg bid
8b		Expansion	Ibr. Intol.	35	A4		$A 4 (N=30) \rightarrow A7 (N=35)$
9		Expansion	RS/PLL	30	A3		$A3 (N=12) \rightarrow A4 (N=30)$
10		Expansion	Ibr. RR	6	A3		A3 (N=16) $\rightarrow$ A4 (N=30) $\rightarrow$ A7 (N=6)

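### SAP Section 12.6 labels average daily dose in mg/day but divides by a duration of exposure that it defines only in months

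*SAP*

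**What the plan says.** SAP Section 12.6 lists four exposure quantities and says that all will be summarised descriptively. Two of them matter here.

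- Duration of exposure: "Duration of exposure (months) is defined as (last dose date first dose date + 1) / 30.4375". The minus sign between the two dates seems to have been lost when the text was extracted from PDF; it is read here as last dose date minus first dose date. The stated unit is months.
- Average daily dose: "Average daily dose (mg/day) is defined as (actual cumulative dose (mg) / duration of exposures". The result is labelled mg/day and the numerator mg. The divisor has no unit and no conversion.

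A third bullet bears on intent. For relative dose intensity the section writes "Relative dose intensity is defined as (total cumulative dose (mg) / (duration of exposure (days", so it names the duration in days there, although it gives no formula for a duration in days. Total cumulative dose, the remaining quantity, is defined in grams, while the average daily dose bullet works in mg.

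**The concern.** A derivation rule should give the unit on its label when its terms are used as defined. Here the only written-out formula for duration of exposure ends in months, and the average daily dose bullet uses that term without qualification. Followed to the letter, the rule gives mg per month.

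What is at stake is one descriptive exposure summary. SAP Section 6.1 plans no formal hypothesis tests, and no response or survival analysis in Section 11.0 uses the average daily dose. The quantity will nevertheless be tabulated, and SAP Section 1.0 gives the SAP precedence over the protocol where the two differ, so clearer wording in the protocol would not automatically govern.

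**Working it through.** The SAP reports no exposure result, so there is no figure to reproduce. The check is one of units.

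**Inputs**
- Duration of exposure in months = D / 30.4375, where D = last dose date − first dose date + 1 in days (SAP Section 12.6).
- Average daily dose = C / duration of exposure, where C is the cumulative dose in mg (SAP Section 12.6).
- Dose for illustration: 200 mg/day, that is 2 × 100 mg. The only legible regimen in the SAP is in the Cohort 8a row of Table 2, "A4 subjects switched to 100 mg bid". It is used for scale only, and constant intake is assumed.

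**General result**
- Rule with the section's own definition: C / (D / 30.4375) = 30.4375 × C / D.
- Quantity on the label: C / D.
- Ratio: 30.4375, free of both C and D.

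**Numbers at 336 days and 200 mg/day**
- C = 200 × 336 = 67,200 mg.
- Duration in months = 336 / 30.4375 = 11.039.
- Rule as defined: 67,200 / (336 / 30.4375) = 6,087.5.
- Rule in days: 67,200 / 336 = 200 mg/day.

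**Other intakes and durations**

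| Assumed intake (mg/day) | Divisor in months, as defined | Divisor in days | Ratio |
|---|---|---|---|
| 100 | 3,043.75 | 100 | 30.4375 |
| 200 | 6,087.5 | 200 | 30.4375 |
| 400 | 12,175 | 400 | 30.4375 |

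Each row is the same at 28, 336 and 1,680 days, because the number of days cancels.

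**The case against.** The best answer is that a unit word is missing and nothing more. The output is labelled mg/day and the numerator mg, so only a divisor in days gives the stated unit. The relative dose intensity bullet in the same list names days outright. The day count is simply the visible formula before division by 30.4375. A 30-fold excess would also be conspicuous in a table, and a programmer would probably correct it unprompted.

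This stands as evidence of intent, and it keeps the point minor. It does not repair the rule. The section marks days where relative dose intensity needs them and leaves the unit off the average daily dose, so the programmer must set aside the section's only definition of the term to reach the labelled unit.

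A reader might go further and infer that the reported average daily dose will be 30 times too large. The document does not support that. It shows a rule that gives the wrong unit if applied literally, not that anyone will apply it so.

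**Conclusion.** The point holds as a minor unit error. With duration of exposure as Section 12.6 defines it, the average daily dose rule yields mg per month, exactly 30.4375 times the labelled mg/day. That factor rests on no assumption about dose or follow-up. Only the illustration at 200 mg/day is assumed. Days were evidently intended, and the effect is confined to a descriptive summary.

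Three neighbouring items might be taken for further errors. None is established.

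- **Relative dose intensity.** As shown, a dose in mg is divided by days times a one-gram factor times 2, so the units do not cancel. That factor stands where a dose would be, doses are blacked out elsewhere in the SAP, and the same list has lost a minus sign. The factor may be damaged by redaction or extraction, so no error and no size can be claimed from it.
- **Month constants.** Section 11.4 uses a slightly different constant, "date of first dose + 1) / 30.4376 and summarized using descriptive statistics". At Day 1680 the difference is 1680/30.4375 − 1680/30.4376 = 0.00018 months, which is negligible.
- **Cohort 2c.** Section 12.6 limits relative dose intensity to "Cohort 2b, 2c, 9, and 10 in which the intended dose regimen/level were never changed per protocol", while the note to the dose-escalation schema contains "Under Amendment 6, subjects in Cohort 2c and in Cohort 4b" after sentences about cohorts that were switched. The words saying what happened to Cohort 2c are blacked out, so no contradiction is shown.

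**What to change.** In SAP Section 12.6:

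1. Add a definition: duration of exposure (days) = last dose date − first dose date + 1.
2. Restate the rule: average daily dose (mg/day) = total cumulative dose (mg) / duration of exposure (days). This also uses one name for the cumulative dose, which the section now calls both total and actual.
3. Keep months for displaying the duration and grams for displaying the cumulative dose, and use neither in the calculation.

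With the divisor in days, the illustration returns 67,200 / 336 = 200 mg/day, as it should. The cost is a few words in the SAP and the matching line in the derivation specification. No new data are needed and no other analysis changes.
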